#### **Primary analysis**

The primary analysis of the impact of the intervention will be a regression model of reading test score at post-test including all data from both cohorts. The model will be estimated with all pupils that completed a pre-test and a post-test.

The primary outcome model will have raw score at post-test as the dependent variable and the following covariates will be included in every model:

- an indicator of whether the pupil is in the Graphogame intervention group. The
  excluded group is the control group, so the coefficient of the intervention group
  indicator measures the difference in (conditional) outcomes between the intervention
  group and the control group
- the pupil's raw score on the pre-test. The coefficient is incidental to the research, but explains a large proportion of outcome variance, increasing the power of the analysis.
- an indicator of which class and intervention cohort the pupil was in, to account for the stratified randomisation. As classes are nested within schools, an indicator for school is not necessary for this single-level model.

The above model will yield the main intervention effect for publication in the executive summary. In addition, a further model will explore the interaction between class and intervention in order to determine whether Graphogame was differentially effective between different classes or schools. This analysis will be somewhat underpowered but will yield interesting results in terms of whether certain classes or schools had larger effects than others.

The sample size and the rate of school and pupil attrition (i.e. the number of schools and pupils analysed compared to the number of schools and pupils that were randomised) will be reported in the CONSORT flow diagram. In an effort to determine whether there was any biased attrition, a summary of the analysed pupils' average characteristics will be reported by randomised group.

#### Interim reporting

An interim analysis will take place at the end of the first year on just the primary outcome. The interim results will be discussed with the EEF Grants Committee, with advice from the Evaluation Advisory Group if required, to determine whether or not the trial should continue. If there is substantial evidence of a positive effect of the intervention then the Grants Committee may advise to move to a larger effectiveness trial, while if there is evidence of negative effects then they may advise to stop the trial. However, the analysis of data from the first year will be underpowered for plausible positive or negative effects and therefore it is most likely that the trial will be completed as planned.

We will use the following rule to decide what to recommend on the basis of the interim analysis:

Interim result	Decision
Significant positive effect (p < 0.0294)	Expand to effectiveness trial
No significant effect (p > 0.0294)	Continue as planned
Significant negative effect (p < 0.0294)	Stop trial

Armitage et al. (1969) were the first to numerically compute the extent to which the type I error probability is increased over its nominal level if a standard hypothesis test is conducted at each of a series of interim analyses. They studied the problem of testing a normal mean with known variance and set the significance level (or type I error probability) for the trial to be 5%. If one interim analysis and one final analysis are performed this error rises to 8%. This is the situation here. Although the final result will not be predicated on a significance level, the decision at the interim analysis is binary and we should therefore adopt an appropriate threshold to aid our decision. The threshold p < 0.0294 is the Pocock boundary for two planned analyses (Pocock, 1977). Were the final analysis to use a significance threshold, it would also need to be p < 0.0294. We will hence construct 97% confidence intervals around the final result and note that any reference to the trial demonstrating a 'significant' result (at either analysis) is still at the conventional level of p < 0.05.

#### Missing data

Missing data presents a problem for analysis, whether a pupil is missing a value for an outcome variable (post-test score) or for covariates (e.g. pre-test score). If outcome data is 'missing at random' given a set of covariates then the analysis has reduced power to detect an effect; if data is 'missing not at random' (for example, differential dropout in the intervention and control groups for unobserved reasons) then omitting these pupils (as in the

primary 'completers' analysis) could bias the results. Imputing missing data could improve the robustness of the analysis and examine how sensitive the results are to alternative assumptions.

If the amount of missing data exceeds 5% of the randomised sample then we will consider using multilevel multiple imputation methods to check whether the results from the 'completers' analysis are sensitive to missing data. A discussion of the results in the context of missing follow-up data will be presented. If follow-up data is missing at random given covariates, and these covariates are included in the model, the results will be unbiased. It may be that the results of the multiple imputation do not differ appreciatively from the completers analysis. If this is the case and we are reasonably confident that covariates explain any missingness then this will complete the primary analysis. Otherwise, some sensitivity analysis (e.g. using extreme values) may be necessary.

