# Sample size

The aim of the study was to recruit 10 Cambridgeshire schools and include year 2 pupils that had not reached the expected standard in the phonics screening check. Eligible pupils would then be randomly allocated to either the intervention or control group (see 'Randomisation'). The same design will be used for two years (2015/16 and 2016/17), doubling the overall sample size.

Initial estimates of statistical power suggested that a total sample size after two years of 400 pupils would be sufficient to detect a standardised effect size of 0.17 with 80% power. For sample size calculations, we assumed a final model without a school-treatment interaction and including a fixed effect for school. This is appropriate since we do not intend to generalise the results of the trial beyond its schools (Feaster et al, 2011). This effect size is smaller than might be expected of the Graphogame programme according to previous small-scale researcher-administered studies, but is appropriately conservative given that previous research had used outcome measures closely aligned to the intervention and that individual researchers sat with children and encouraged them to persist on task while they played Graphogame.

Cambridge was able to recruit 11 schools in the first year, from which 216 pupils were tested at baseline and allocated to a group. Given that we might expect up to 10 per cent attrition, this is in line with our expectations of the achieved sample size for the first year. We anticipate the sample size being similar in the second year of the study.

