### **Randomisation**

An NFER statistician performed a stratified randomisation of pupils by class with the aim of balancing the randomisation at class level (i.e. having equal numbers in intervention and control groups within each class) to aid delivery. We first put schools in a random order; within school we put classes in a random order; and within classes we put pupils in a

<sup>1 Use of the Level 1B test was a change to the original protocol. See 'primary outcome' section.

<sup>2 Assuming a two-tailed test with a 95% confidence level, number of schools=10, expected number of pupils per school=20, intra-school correlation=0 (pupil randomisation), correlation between pre- and post-test scores=0.8.

random order. The number of classes per school varied from one to three. The entire list was then allocated to control and intervention in turn: first pupil to control, second to intervention, third to control, and so on. The SPSS syntax used to randomise pupils in the first year is shown in Appendix 1, and similar syntax will be used in the second year.

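### With only post-tests missing and no auxiliary variables named, imputation will match the completers analysis, so their agreement is no evidence against not-at-random dropout

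*SAP*

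**What the plan says.** The primary model (SAP, Primary analysis) regresses post-test score on group, pre-test score and class/cohort indicators, using pupils who have both tests. The Missing data section warns that leaving pupils out could bias this analysis if loss is not at random, for example if the arms lose pupils differently for unobserved reasons. It presents imputation as a way to see how far results depend on alternative assumptions.

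If more than 5% of the randomised sample is missing, the team will consider multilevel multiple imputation. On bias under the at-random assumption, the section states: "If follow-up data is missing at random given covariates, and these covariates are included in the model, the results will be unbiased".

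It then allows that imputation and completers could turn out much alike, and sets the condition under which the work may stop there: "If this is the case and we are reasonably confident that covariates explain any missingness then this will complete the primary analysis".

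If those conditions are not met, some sensitivity analysis, such as one with extreme values, is described as possibly needed. The section gives no imputation variables, no size of difference that would count as appreciable, and no basis for judging confidence in the covariates.

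On attrition, the Primary analysis section promises CONSORT counts and a summary of the analysed pupils, whose "average characteristics will be reported by randomised group".

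**The concern.** The stopping rule has two parts: agreement between two analyses, and a judgement about the covariates. The agreement part looks like evidence, but standard multiple imputation assumes missingness at random given its covariates, and the completers regression is unbiased under that same assumption, as the section itself says. Comparing the two does not vary the assumption in doubt. If their agreement is read as reassurance, an effect distorted by selective loss could be reported as robust, and the one analysis that would vary the assumption need not be run. The SAP expects up to 10% attrition against a 5% trigger, so the rule may well come into use.

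**Working it through.** **1. Design figure.** Footnote 2 to the Sample size section gives the inputs: "Assuming a two-tailed test with a 95% confidence level, number of schools=10, expected number of pupils per school=20" and "correlation between pre- and post-test scores=0.8".

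- Residual SD = √(1 − 0.8²) = 0.6.
- Standard error with 200 per arm = 0.6 × √(2/200) = 0.06.
- Detectable effect = (1.960 + 0.842) × 0.06 = 0.168.
- Power at 0.17 = 0.809; total needed for 80% = 392.

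This reproduces the SAP's statement that a "total sample size after two years of 400 pupils would be sufficient to detect a standardised effect size of 0.17 with 80% power". The yardstick below is 0.17 SD.

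**2. What is missing.** Year 1 had 11 schools, "from which 216 pupils were tested at baseline and allocated to a group", so the pre-test is known for those pupils and loss is essentially of the post-test. A similar year 2 gives 2 × 216 = 432 pupils. Ten per cent of these is about 43; the 5% trigger is 21.6, so 22 pupils. The spelling test is sat together with the reading test, so it will usually be missing too.

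**3. Why the analyses agree.** Let X_o and X_m be the covariate rows of pupils with observed and missing post-tests, y_o the observed scores, and b the completers estimate, so that X_o′y_o = X_o′X_o b. Imputation from the same covariates fills the missing scores around X_m b. Averaged over many imputations, the refitted coefficient is

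(X_o′X_o + X_m′X_m)⁻¹ (X_o′X_o b + X_m′X_m b) = b.

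The reason for dropout does not appear in this identity. Only simulation noise separates the two estimates.

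**4. Simulation.** 400 replicates; 432 pupils; about 10% of post-tests missing overall; pre-test complete; true effect 0; 50 imputations. The 40 classes, the dropout mechanisms and the auxiliary variable are assumptions. Estimates are in SD units.

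| Dropout mechanism | Completers | Imputation, same covariates | Imputation plus auxiliary |
|---|---|---|---|
| Depends on pre-test, both arms | −0.001 | −0.002 | 0.000 |
| Depends on pre-test, intervention arm only | 0.001 | 0.001 | 0.000 |
| Depends on unexplained outcome, intervention arm only (14.5% v 5.9% lost) | 0.120 | 0.120 | 0.063 |
| Depends on the auxiliary, intervention arm only (14.9% v 5.9% lost) | 0.087 | 0.087 | 0.001 |

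The same-covariate gap had a standard deviation of about 0.003 and a maximum of 0.011 in every scenario. Standard errors were also the same, about 0.06. The auxiliary was assumed to explain half the residual variance.

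A second simulation (200 trials, 44 assumed classes, true effect 0.17, 11% v 8% lost with outcome-related selection in one arm) gave completers 0.223 and imputation 0.222, against 0.168 with full data. The bias is 0.223 − 0.168 = 0.055, with a mean absolute gap of about 0.003.

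**5. Size without simulation.** If a fraction p of one arm is lost and those pupils lie δ SD from the at-random prediction, the effect moves by p × δ. The values of δ are assumptions.

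| p | δ = 0.3 | δ = 0.5 | δ = 1.0 |
|---|---|---|---|
| 5% | 0.015 | 0.025 | 0.05 |
| 10% | 0.03 | 0.05 | 0.10 |
| 15% | 0.045 | 0.075 | 0.15 |

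At p = 10% and δ = 0.5, the shift is 0.05, and 0.05/0.17 = 29%. With loss in both arms, the shift is the difference between the two products, so equal loss of the same kind cancels.

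**The case against.** A reader might infer that the SAP accepts agreement alone and leaves biased dropout undetected. It does not say that. Stopping also requires confidence that covariates explain the missingness, which is the at-random judgement itself; failing that, extreme-value analysis may follow. The section also promises a discussion of results in the light of missing follow-up data. This objection stands, and it narrows the point: the second condition has no criterion, the observed data cannot verify it, and the fallback is optional.

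A reader might also infer that the two analyses must always coincide. The identity above holds only if the imputation model adds nothing to the analysis model. The SAP leaves the variable list open, and FSM status lies outside the primary model; how much it would help was not tested. A strong auxiliary did move the imputed estimate, although it left about half the bias when dropout depended on the unexplained outcome. A multilevel imputation model may also differ slightly from the fixed-class regression.

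Nor do the documents show that every randomised pupil has a pre-test. They show it for year 1 only, and the Missing data section allows for missing pre-test scores, where imputation can recover information.

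A bias of a third or more of 0.17 is not established as likely. The 11% v 8% scenario gives 0.055/0.17 = 32%. The 0.120 result (about 70% of 0.17) needs strong one-sided selection with overall loss at the plan's ceiling: (14.5 + 5.9)/2 = 10.2%. An outcome 0.5 SD off prediction is 0.5/0.6 = 0.83 residual SDs, which is not small. Both arms share classes and test administrators were not told the allocation, so nothing in the SAP predicts such selection.

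Finally, comparing analysed pupils by group, with CONSORT counts, can reveal differential loss on measured characteristics. A table of lost against retained pupils would add to that, but it could not detect selection on unobserved ones either.

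**Conclusion.** The point holds in a conditional form. Where only post-tests are missing and the imputation model adds no informative variable to the analysis covariates, agreement between imputation and completers is close to automatic and is no evidence against the not-at-random dropout that the section names. As written, the SAP meets the first condition for year 1 and does nothing to rule out the second. What then protects the result is a judgement without a criterion and an optional fallback.

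The near-zero gap follows from algebra and did not depend on the dropout mechanism. The size of any bias rests wholly on assumed selection. The 29% illustration takes the SAP's own upper attrition figure in one arm and an assumed 0.5 SD departure. A shift of 0.05 SD is a little under one standard error (about 0.06), so it matters for a modest effect but would not by itself overturn a clear one. This is a worthwhile tightening of a plan that already recognises the threat, not a flaw that invalidates the primary analysis.

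**What to change.** Revise the Missing data section as follows.

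- If more than 5% of post-tests are missing, run a delta-adjusted (pattern-mixture) analysis whether or not imputation agrees with completers. Shift the imputed post-tests separately by arm over a range stated in advance, for example −0.5 to +0.5 SD, labelled as an assumption.
- Report how the effect size and the 97% interval move, including the shift at which the interval first includes or excludes zero. Present this as description, because the Interim reporting section says the final result does not rest on a significance level.
- Specify the imputation model and name any auxiliary variables, for example FSM status. Say that agreement with completers under the same covariates is expected and is not a test of the at-random assumption.
- Tabulate pre-test means of lost and retained pupils by arm beside the planned summary of analysed pupils.

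The cost is a few lines of SAP text and a little extra analysis on data the plan already collects. The downside is a less definite statement of robustness in the report.

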## **Pre-specified secondary analysis**

- 1. Analysis of differential impact on FSM pupils: the primary analysis models will be estimated for the sub-sample of pupils that have been FSM since starting school (the indicator of Pupil Premium status). The effect size will be measured in the same way as above. The standard deviation will be re-estimated for the FSM-only sample to use for standardising the estimated effect size. We will also estimate an FSM-by-intervention interaction model to analyse the differential impact of the intervention on FSM pupils.
- 2. Analysis of differential impact by pupil ability: the primary analysis model will be run with the addition of an interaction between pre-test score and the intervention group indicator.
- **3. Impact on spelling:** the primary analysis models will be run with Single Word Spelling Test raw scores as an outcome variable.

#### **Sensitivity Analysis**

We will carry out analysis of the primary outcome using a multilevel model with class and class-by-intervention interaction as random effects. Class will be uniquely numbered. We will test whether the class by intervention interaction is significant. If not, the effect size itself (without the interaction term) should be the same as that from the fixed effects model. If it is significant, this will tell us something about the extent to which the effectiveness of the intervention varies depending on which class it is delivered in. Were we trying to generalise to a wider population of schools, this would be important to take into account. Since we are not seeking to generalise results beyond the schools in this effectiveness trial, the effect size and confidence interval from the fixed effects model (without interaction) will still serve as the definitive result of the trial.

## **Exploratory analysis**

Exploratory analyses will focus on the implementation of the intervention to attempt to understand *how* the intervention worked rather than *whether* it worked. Differences in the way the intervention was implemented across schools were at the discretion of school staff and researchers on the Cambridge team, so this analysis cannot be definitively interpreted

as causal. However, the analysis may give clues as to what drives any effect that may be identified by the impact analysis. It will investigate whether different approaches to implementation led to different amounts of progress made by pupils.

We will conduct an on-treatment analysis of the number of hours spent using Graphogame. Pupil-level game usage data will be recoded into levels of programme fidelity (shown in Table 1). We will explore the differential impact of the intervention by fidelity level by including indicator variables for each fidelity level as well as the intervention group indicator. It will also be analysed without recoding, to give an indication of the amount of impact an additional hour of using Graphogame made to reading.

Whilst this analysis appears attractive, it is very vulnerable to bias as those individuals who used the program the most are likely to have other characteristics that are associated with improved test performance. To mitigate this, Complier Average Causal Effect analysis (Sussman and Hayward, 2010) will be carried out using a continuous variable to describe dosage.

Table 1 Classification of programme fidelity

Level of programme fidelity	Total number of hours spent on Graphogame Rime
Low	0-3
Medium	3-6
High	6-10
Very high	More than 10

# **Appendix 1 – Randomisation syntax**

```
Title 'Pupil randomisation'.
get file = "I:/EERR/First year/Definitive list of eligible pupils.sav".
* Set randomisation seed.
set rng=mt, mtindex=08122015.
* Randomise school order.
compute schrand=rv.uniform(0,1).
sort cases by NFERNO.
aggregate outfile = "c:/temp/schools.sav" /break = NFERNO
 /sch = first(schrand).
match files /file = * /table = "c:/temp/schools.sav" /by NFERNO.
* Randomise class order.
compute clsrand=rv.uniform(0,1).
sort cases by NFERNO Class.
aggregate outfile = "c:/temp/class.sav" /break = NFERNO Class
 /cls = first(clsrand).
match files /file = * /table = "c:/temp/class.sav" /by NFERNO Class.
* Create variable for randomising pupils.
compute rand=rv.uniform(0,1).
* Stratify randomisation by class.
sort cases by sch cls rand.
* Allocate pupils to groups by order.
compute group = MOD($casenum,2).
variable labels group = "Group allocation".
```

value labels group 0 'Control group' 1 'Intervention group'.

\* Group split overall. frequencies group.

\* Group split by school/class.

crosstabs NFERNO by group.

crosstabs Class by group by NFERNO.

sort cases by NFER\_PUPIL\_ID.

save outfile = "I:/EERR/First year/Randomisation.sav".
